## 397 **6. Equipment Pickup Visit**

### 398 **6.1 Prescription Glasses**

399 Participants will come back for their Equipment Pickup Visit once the study team has received the  
400 glasses shipment from Zenni. These lenses must be used in conjunction with the lamp, therefore must be  
401 picked up alongside the lamp.

### 402 **6.2 Study Lamp**

403 Participants will receive their lamp at this visit. Patients were randomized at the  
404 enrollment/randomization visit and are prepared to receive their respective lamp. The study coordinator  
405 will instruct the participant and guardian on the use and setup of the lamp. The HOBO sensor will be  
406 attached to the lamp, and participants and guardians will be instructed on how to remove the sensor  
407 from the lamp to bring to follow-up visits.

### 408 **6.3 HOBO Sensor**

409 Participants will receive the HOBO sensor attached to their lamp. The sensor will be removable to bring  
410 to follow-up visits. Participants and guardians will be instructed how to remove the sensor properly, and  
411 how to put it back on the lamp.

### 412 **6.4 Automated Wall Plug-In**

413 Participants will receive an outlet timer that will be set to the times the parent or guardian has specified  
414 to be their on (dawn) and off (dusk) times. It will be during these times that the child will be asked to be

415 in the room with the light on for at least one hour at dawn and one hour at dusk. This will allow the lamp  
416 to turn on and off automatically during the designated times.

## 417 **6.5 Testing Not Completed at Enrollment**

418 Participants that were unable to complete testing at the enrollment visit due to unavailability of  
419 equipment may have this testing performed at this visit.

- 420 • Axial length measurement (see 4.7.3)
- 421 • OCTA (see 4.7.4)

## 422 **7. Follow-Up**

### 423 **7.1 REDCap Daily Surveys**

424 Each day, the parent or guardian of the participant will receive a survey via email with two questions as  
425 to what times the lamp was used during the dawn hours and dusk hours that day. Parents and guardians  
426 will be reminded of the importance of this survey during telephone calls and follow-up visits.

427 This survey will serve as a second point of compliance data to compare to the data received from the  
428 HOBO sensor.

### 429 **7.2 Telephone Calls**

430 Telephone calls will be made by the study coordinators to the participants and guardians at 2 weeks ( $\pm$  3  
431 days), 3 months ( $\pm$  1 month), and 9 months ( $\pm$  1 month) post Equipment Pickup visit.

432 Coordinators will contact parents to confirm that the BIOS SkyView/Aooshine lamp is working properly,  
433 encourage compliance, and question the parent as to whether the child is experiencing any issues with  
434 treatment.

435 Additionally, these calls will help maintain direct contact with the parents of the participants, develop  
436 and maintain rapport with the family, and assist with scheduling of study visits if needed.

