## 218 **1.8 Study Objective**

219 The purpose of this short-term, pilot, randomized trial is to investigate the efficacy of violet light  
220 exposure through the BIOS SkyView Lamps at dawn and dusk versus non-violet light exposure through  
221 Aooshine Bedside Lamps in slowing the progression of myopia in school aged children as an alternative  
222 to current clinical treatments to determine whether to proceed to a full-scale longer-term randomized  
223 trial. This decision will be based primarily on assessing responses to light exposure by comparing  
224 treatment groups on the following outcomes:

- 225 • Axial length elongation
- 226 • Spherical refractive error
- 227 • Quality of life
- 228 • The proportion of participants reporting adverse effects
- 229 • The proportion of participants reporting >75% light exposure compliance

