## 384 **5. Randomization**

### 385 **5.1 Randomization Process**

386 Participants eligible for randomization will be randomly assigned in a 1:1:1 distribution respectively to:

- 387 • Violet light experimental group (BIOS SkyView Lamp) with polycarbonate glasses
- 388 • Violet light experimental group (BIOS SkyView Lamp) with CR-39 glasses
- 389 • Non-violet control group (Aooshine Bedside Lamp) with CR-39 glasses

390 The investigator will construct a separate Master Randomization List using a permuted block design  
391 stratified by the treatment group. A participant is considered randomized when REDCap randomization  
392 process is completed.

393 The participant, parents, testers, and investigators will be masked to treatment group. If the need arises,  
394 the investigator may become unmasked after discussion of a specific case with the study team in  
395 response to any adverse events. The study coordinator will remain unmasked to the treatment group in  
396 order to facilitate the type of equipment and lenses the participant will need.

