## 531 **9.2 Decision Guideline**

532 The data collected in this short-term, pilot randomized clinical trial will primarily be used to determine  
533 whether to proceed to a full-scale, longer-term randomized trial of violet light vs control non-violet. The  
534 side effect profiles in the experimental and control groups will also be considered when deciding  
535 whether to proceed with a full-scale trial.

536 The decision guideline for determining whether to proceed to a full-scale randomized trial will be based  
537 on the primary and secondary outcomes at study conclusion.

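### Coordinators unmasked for equipment logistics also make the calls that ask about treatment problems and encourage lamp use, and the protocol does not say whether call answers count toward the adverse-effect outcome

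*Protocol*

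**What the plan says.** Section 5.1 (Randomization Process) sets the masking: "The participant, parents, testers, and investigators will be masked to treatment group". It then makes one standing exception: "The study coordinator will remain unmasked to the treatment group in" "order to facilitate the type of equipment and lenses the participant will need". No other purpose is given.

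Section 7.2 (Telephone Calls) assigns the calls: "Telephone calls will be made by the study coordinators to the participants and guardians at 2 weeks", with further calls at 3 and 9 months, all counted from the Equipment Pickup visit. Besides checking that the lamp works, the callers are to "encourage compliance, and question the parent as to whether the child is experiencing any issues with" treatment. Section 7.1 adds that the calls are used to remind parents of the importance of the daily lamp-use survey.

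Section 1.8 (Study Objective) says of proceeding to a full-scale trial: "This decision will be based primarily on assessing responses to light exposure by comparing" the treatment groups on five outcomes. One is "The proportion of participants reporting adverse effects"; another is the proportion reporting compliance above 75%. Section 9.2 (Decision Guideline) repeats that "side effect profiles in the experimental and control groups will also be considered when deciding" whether to go on.

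Adverse effects are also asked about at the 6- and 12-month visits (Section 7.3) and at each study visit (Section 9.3). Neither section names the role that asks.

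**The concern.** The reason given for unmasking the coordinator is logistical, but the calls go beyond logistics. They put an open question about treatment problems, and an instruction to encourage use, in the hands of the one role known to be unmasked.

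Someone who knows that a child has the violet lamp may, without intending to, probe further for eye complaints than when calling a control family, or press harder for lamp use. If answers to the open question count as adverse-effect reports, the arms could differ on that outcome with no true difference in tolerability. If encouragement differs, actual lamp use or survey completion could differ by arm. Both outcomes are among the five that inform the decision on a full-scale trial.

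**Working it through.** The plan states no figure on this point, so the check is mainly a comparison of roles and data sources.

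1. **Who calls, and what they know.** The caller is the study coordinator (Section 7.2), who is the only role stated to be unmasked (Section 5.1). The stated reason covers equipment and lenses. It does not cover eliciting symptoms or encouraging use.

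2. **Share of contacts.** After pickup, the scheduled contacts at which problems are asked about are the calls at 2 weeks, 3 months and 9 months (Section 7.2) and the visits at 6 and 12 months (Section 7.3). The unmasked role makes 3 of these 5, including the two that come before the first follow-up visit.

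3. **Adverse effects.** Section 7.3 sends visit data to a Follow-Up Visit form. Section 7.2 names no form for the calls. Nothing states whether call answers enter the Section 1.8 proportion, which leaves two cases:
   - Call answers count. Part of the outcome is then elicited with knowledge of the arm.
   - Call answers do not count. The comparison then rests on the visits, and this route to bias from the calls is closed.

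4. **Compliance.** It is measured by the occupancy sensor read at visits (Section 7.3) and by the daily emailed parent survey (Section 7.1). The caller scores neither. What remains is indirect: unequal encouragement could change actual lamp use, and unequal reminders could change survey completion. The sensor limits error in measuring use but does not prevent use itself from being influenced.

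5. **Primary outcome.** Section 9.1 uses cycloplegic autorefraction, and Section 5.1 masks the testers. An effect could arise only indirectly, through lamp use that differs by arm.

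6. **Scale.** With up to 24 per arm (Section 4.4), one additional reporter changes an arm's proportion by 1/24 = 4.2 percentage points. If the two violet arms are pooled, as the violet versus non-violet contrast in Section 9.1 would allow, one reporter changes the pooled proportion by 1/48 = 2.1 points. These figures show how sensitive the proportions are to a single report. They do not estimate bias.

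**The case against.** Several points on the other side have force.

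- **The calls are not described as adverse-event collection.** Section 7.2 presents them as lamp checks, encouragement, rapport and scheduling, and adverse-effect questioning is written into the visits. This stands: no section routes call answers into the Section 1.8 outcome. The concern about adverse effects is therefore conditional. But no section excludes call answers either, and the call question covers the same ground.

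- **The caller does not measure compliance.** This also stands. A reader might infer that compliance is open to differential questioning. The sensor and the parent survey rule that out and leave only encouragement and prompting.

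- **Visit questioning treats the arms alike.** A reader might argue that the comparison is unsound even if call answers are excluded, because parents must then recall complaints over months. Long recall can lose transient complaints, but it does so in all three arms, so it gives no reason to expect a difference between them. It is a separate matter from the unmasked caller.

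- **A script may exist elsewhere.** Section 4.7 refers to a manual of procedures that is not at hand. The protocol's silence therefore does not show that questioning is unstandardised, only that the protocol does not require it to be standardised.

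- **There is a practical reason for the allocation.** The arms use two different lamp products, and a masked caller discussing a lamp fault could learn the arm. This is a fair argument for keeping the coordinator on the calls. It is no argument against fixed wording or against collecting adverse effects by another route.

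**Conclusion.** The role conflict is plain in the text: a person unmasked for equipment purposes is given open-ended questioning about treatment and encouragement of use, and the protocol states no safeguard. The consequence for the adverse-effect comparison depends on call answers being counted, which the protocol does not settle. For compliance the route is weaker and indirect. Measurement of the primary refractive outcome is not directly affected.

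No size of bias can be derived, because it would require detection rates by arm that the document does not give. Nor does the document support concluding that the adverse-effect comparison is biased whichever way the calls are treated, or that the trial's main result is compromised. The point merits a change because side effects inform the decision to proceed, a single report moves a 24-child arm by 4.2 points, and who asks what is a matter of conduct that analysis cannot repair afterwards.

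**What to change.** - **Section 7.2:** keep the coordinator's calls and the live question about problems, but require one fixed script with the same wording in all arms for that question, for the compliance encouragement and for the survey reminder.
- **Section 7.1:** at the three call times, send parents an identical adverse-effect checklist through the existing REDCap survey.
- **Sections 7.3 and 9.3:** have the masked investigator ask the same checklist at the 6- and 12-month visits.
- **Sections 1.8 and 9.2:** state that the arm comparison of adverse effects rests on the checklist reports. Record problems volunteered to the coordinator for safety, flag them by source, and report them separately from that comparison.

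The cost is a wording change, a call script, one short form and a few minutes of parent time at three points. No additional staff or visits are needed.

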### 437 **7.3 Follow-Up Visits: 6-Month and 12-Month**

438 The following will be performed at Follow-Up Visits and recorded in the Follow-Up Visit CRF via Redcap.

- 439 - Medical History
  - 440 ○ Includes questioning about the occurrence of adverse effects of treatment. Concomitant
  - 441 medications will be recorded, as well as current eyeglasses or contact lenses correction.
- 442 - Compliance Assessment (HOBO sensor data collection)
  - 443 ○ App data will be reviewed and assessments of compliance will be recorded on the
  - 444 Follow-up Examination Form.
- 445 - Standard Refraction
  - 446 ○ The investigator may use their standard refraction technique (with or without
  - 447 cycloplegia) at any time during the visit to ensure that refractive correction meets study
  - 448 criteria at each visit.
- 449 - Cycloplegic Autorefracton
  - 450 ○ See 4.7.2

- 451 - Binocular Near Visual Acuity
- 452     ○ Binocular near visual acuity is measured with participant wearing current refractive
- 453     correction prior to administration of cycloplegia.
- 454 - Distance Visual Acuity
- 455     ○ Monocular distance visual acuity tested at the start of the exam without cycloplegia in
- 456     current correction.
- 457     ○ Measurement of best corrected visual acuity in each eye by a study certified visual
- 458     acuity tester using the E-ETDRS testing protocol.
- 459     ○ If the vision is more than one line ( $\geq 5$  letters) worse than baseline, retest using trial
- 460     frames or phoropter with the most recent subjective refraction.
- 461 - Monocular Amplitude of Accommodation
- 462     ○ Measured in their current correction without cycloplegia with a study-specified and
- 463     provided accommodation near-point rule.
- 464     ○ Axial Length Measurement (12-Month Only)
- 465     ○ See 4.7.3
- 466 - OCTA- Performed (12-Month Only)
- 467     ○ See 4.7.4

#### 468 **7.4 Management of Refractive Error**

469 Spectacle correction must be updated whenever the investigator’s standard refraction technique reveals  
470 a change in refractive error. A change in refractive error is defined as any of the following amounts:

- 471     • A difference of  $>0.75D$  sphere
- 472     • A difference of  $>0.75D$  cylinder
- 473     • A difference of  $>0.50D$  in SE anisometropia
- 474     • A difference in axis of 6 degrees or more when the cylinder is  $\geq 1.00D$ .

475 Whether to update the correction for smaller differences in refraction is at investigator discretion.  
476 updated, the refractive correction must meet the requirements described in section 4.7.

#### 477 **7.5 Non-Randomized Treatment Other than Refractive Correction**

478 Non-randomized treatment for myopia other than changes in refractive error as described above is not  
479 permitted during the study. The investigator must call the principal investigator to discuss the case and  
480 obtain approval for an exception prior to initiating non-randomized treatment (including OrthoK, rigid  
481 gas permeable, and other contact lenses being prescribed for myopia management).

#### 482 **7.6 General Considerations**

483 The study is being conducted in compliance with the policies described in the study policies document,  
484 with the ethical principles that have their origin in the Declaration of Helsinki, with the protocol  
485 described herein, and with the standards of Good Clinical Practice.

486 Data will be directly collected in electronic CRFs, which will be considered the source data.

487 A risk-based monitoring approach will be followed, consistent with the FDA “Guidance for Industry  
488 Oversight of Clinical Investigations – a Risk-Based Approach to Monitoring” (August 2013).

## 489 **8. Miscellaneous Considerations**

### 490 **8.1 Participant Withdrawals**

491 Parents may withdraw their child from the study at any time. If the parents indicate that they want to  
492 withdraw their child from the study, the investigator should attempt to speak with the parents personally  
493 to determine the reason. If their interest is in transferring the child's care to another eye care provider,  
494 every effort should be made to comply with this and at the same time, try to keep the participant in the  
495 study under the new provider's care.

### 496 **8.2 Discontinuation of Study**

497 The study may be discontinued by the study team prior to the pre-planned completion of enrollment  
498 and follow-up for all participants.

### 499 **8.3 Payment to Participants**

500 The parent/guardian of each participant will be compensated \$50 by ClinCard upon completion of the  
501 Enrollment/Randomization Visit, Equipment Pickup Visit, 6-Month Visit, and 12-Month Visits, for a  
502 maximum of \$250.

### 503 **8.4 Costs Covered by the Study**

504 The study will pay for the office visits that are part of the study (Enrollment/Randomization Visit,  
505 Equipment Pickup Visit, 6-Month Visit, and 12-Month Visit).

506 The study will pay for the following:

- 507 • BIOS SkyView/Aooshine lamp will be provided to each participant at no cost.
- 508 • Eyeglasses will be ordered at enrollment (if needed).
- 509 • Frames and Lenses will be ordered by the study team from Zenni.
- 510 • Lens changes will be provided at 6 months if a change is required, and the lenses will be ordered  
511 by the study team through Zenni.

### 512 **8.5 Costs Not Covered by the Study**

513 The study will not pay for eyeglasses obtained elsewhere (the study pays for glasses if needed through  
514 Zenni only). The study will not pay for contact lenses.

## 515 **9. Data Storage and Analysis**

### 516 **9.1 Analysis**

#### 517 Primary Analyses

518 The primary analysis will be an experimental vs control group comparison of change from baseline to 12  
519 months in spherical equivalent refractive error (SER), as measured using cycloplegic autorefraction. At  
520 baseline and all follow-up visits, the mean of the three readings from autorefraction in each eye will be  
521 calculated and then the mean of both eyes for each participant will be used for the analysis. If fewer  
522 than 3 readings are available in each eye, the mean of available readings will be used for each eye to  
523 obtain the mean of both eyes for each participant.

524 The treatment group difference (violet vs. non-violet light) and a 95% confidence interval will be  
525 calculated based on the model estimates at 12 months.

## 526 Secondary Analyses

- 527 • Difference in change in axial length at 6 and 12 months between the violet and non-violet light  
528 group
- 529 • Compliance will be assessed at each follow up and described as excellent (76%-100%), good  
530 (51%-75%), fair (26%-50%) or poor (<25%).

## 531 **9.2 Decision Guideline**

532 The data collected in this short-term, pilot randomized clinical trial will primarily be used to determine  
533 whether to proceed to a full-scale, longer-term randomized trial of violet light vs control non-violet. The  
534 side effect profiles in the experimental and control groups will also be considered when deciding  
535 whether to proceed with a full-scale trial.

536 The decision guideline for determining whether to proceed to a full-scale randomized trial will be based  
537 on the primary and secondary outcomes at study conclusion.

## 538 **9.3 Data Safety Monitoring Plan**

539 The participants in this study are patients routinely seen by the investigator or his colleagues as part of  
540 standard clinical care at CCHMC, Division of Pediatric Ophthalmology. Participants will continue to be  
541 followed clinically by either the investigator or the referring clinicians in addition to attending the study  
542 visits.

543 During the study, participants are observed closely to detect occurrences of any adverse events or  
544 complications that may have arisen. At each study visit, the participants and their guardians will be asked  
545 questions regarding the occurrence of adverse events to determine whether any complications or  
546 adverse events might have occurred since the previous visit.

547 In the case of a suspected adverse event, further testing may be performed, and non-study treatment  
548 may be initiated to ensure patient safety.

## 549 **9.4 Source Documents and Case Report Forms**

550 Adequate records will be maintained for the study including participant medical records, test reports,  
551 signed informed consent forms, adverse event reports, and information regarding participant  
552 discontinuation and reasons for discontinuation. All original source documentation will be stored  
553 electronically in the password-protected CCHMC shared-drive or in a locked filing cabinet located in the  
554 investigator's office or research coordinator's workspace.

555 In accordance with 21 CFR 50, guardians will provide written informed consent for participation in this  
556 study.

## 557 **9.5 Changes to Protocol**

558 The investigator will notify the IRB of any unanticipated problem requiring a change in the protocol to  
559 eliminate apparent immediate hazard to a subject per CCHMC Research Policy, R-18. Changes that affect

560 the scientific soundness of the study or the rights, safety, or welfare of human subjects will be submitted  
561 to the IRB in an amendment prior to implementation.

562

563

564

565

